6. TREATMENT PROCEDURES

6.1 Classification of Product(s), Medical Device(s), and/or Combination Product(s)

The Amgen IPs used in this study include AMG 596, AMG 404 and intravenous solution stabilizer (IVSS).

The Investigational Product Instruction Manual (IPIM), a document external to this protocol, contains detailed information regarding the storage, preparation, destruction, and administration of AMG 596 and AMG 404.

The medical devices used in this study include: infusion pump, IV bag, and infusion line including a 0.2 µm in-line filter.

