6.2.3 Dose Escalation, Stopping Rules and Dose-limiting Toxicities (DLTs)

The preliminary estimate of MTD will use BLRM design. Refer to [Section 10.2](#) for further details of stopping rules.

A DLT will be defined as any of the following occurring in a subject during the DLT period (first [REDACTED] treatment days for both AMG 596 monotherapy and in combination with AMG 404) and regarded to be related to AMG 596 and/or AMG 404. For adverse event severity grading see [Section 9.2](#) (Adverse Events). The Common Terminology Criteria for Adverse Events (**CTCAE version 4.0**) will be used to assess toxicities/adverse events with the exception of cytokine-release syndrome (CRS) with grading performed according to the recommendations provided in [Appendix E](#).

Hematological DLTs

- ANC < $0.5 \times 10^9/L$ for ≥ 7 days
- Febrile neutropenia (fever of unknown origin without clinically or microbiologically documented infection) with ANC < $0.5 \times 10^9/L$ and fever $\geq 38.5^\circ C$

- Platelets $< 50 \times 10^9/L > 7$ days or clinically significant bleeding
- Lymphopenia of any grade is not considered a DLT

Non-hematological DLTs

- Any grade 4 non-hematological toxicity
 - Laboratory parameters of grade ≥ 3 , not considered clinically relevant, and improved to grade ≤ 2 within 72 hours will not be considered DLT (for ALT and GGT elevations grade ≥ 3 , not considered clinically relevant, and improved to grade ≤ 2 within 7 days due to the long half-life of these parameters)
- Any grade 3 or higher non-hematological toxicity if:
 - Nausea and vomiting, which is refractory to anti-emetics
 - Flare-up of pain because of potential increase in tumor volume is not regarded as a DLT
 - Grade 3 non-hematologic toxicity lasting > 3 days despite appropriate treatment
 - Grade 3 fatigue will not be classified as DLT, irrespective of duration
 - Grade 3 acute kidney injury
 - Any grade 3 seizure, ataxia or encephalopathy
 - Other grade 3 neurologic-related adverse events lasting > 3 days despite appropriate treatment
 - Neurologic-related adverse event leading to treatment interruption that needed more than 1 week to resolve to CTCAE grade ≤ 1
 - Any grade 3 endocrinopathy that cannot be adequately controlled by hormonal replacement

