10.5 Planned Methods of Analysis

10.5.1 General Considerations

The analyses described below will be reported separately for subjects enrolled to Arm 1 and for subjects enrolled to Arm 2. Unless otherwise specified, the analyses will be done using the Safety Analysis Set.

Descriptive statistics will be provided for selected demographics, safety, PK, PD, efficacy and biomarker data by dose, dose schedule, and time as appropriate. Descriptive statistics on continuous data will include means, medians, standard deviations and ranges, while categorical data will be summarized using frequency counts and percentages. ORR will be presented with 80% Clopper-Pearson exact CI using the RANO Evaluable Analysis Set. PFS will be summarized using Kaplan-Meier method. Graphical summaries of the data may also be presented.

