3.5 Treatment Schema

For treatment schema, pls. refer Figure 1 & Figure 2 from the protocol.

4. Covariates and Subgroups

Due to the small sample size, the impact of baseline characteristics on study outcomes will not be explored, and no subgroup analyses will be performed.

5. Definitions

Adverse Event (AE):

An adverse event is defined as any untoward medical occurrence in a clinical trial subject.

Dose Limiting Toxicity:

The grading of adverse events will be based on the guidelines provided in the common Terminology Criteria for Adverse Events (CTCAE) version 4.0 available online at <http://evs.nci.nih.gov/ftp1/CTCAE/About.html>).

Also, the grading for Cytokine Release Syndrome (CRS) will be performed according to the recommendations provided by [Lee et al, 2014](#) (Appendix E of the protocol).

A Dose Limiting Toxicity (DLT) is defined as any adverse event meeting the criteria listed below occurring during the first ■ days in each dose exploration cohort and attributable to AMG 596:

Hematological DLTs

- ANC < $0.5 \times 10^9/L$ for ≥ 7 days
- Febrile neutropenia (fever of unknown origin without clinically or microbiologically documented infection) with ANC < $0.5 \times 10^9/L$ and fever $\geq 38.5^\circ C$
- Platelets < $50 \times 10^9/L$ > 7 days or clinically significant bleeding

Non-hematological DLTs

- Any grade 4 non-hematological toxicity
- Any grade 3 or higher non-hematological toxicity if:
 - Nausea and vomiting, which is refractory to anti-emetics
 - Flare-up of pain because of potential increase in tumor volume is not regarded as a DLT
 - Grade 3 non-hematologic toxicity lasting > 3 days despite appropriate treatment
 - Grade 3 fatigue will not be classified as DLT, irrespective of duration
 - Grade 3 acute kidney injury
 - Any grade 3 seizure, ataxia or encephalopathy
 - Other grade 3 neurologic-related adverse events lasting > 3 days despite appropriate treatment
 - Neurologic-related adverse event leading to treatment interruption that needed more than 1 week to resolve to CTCAE grade \leq 1

Any adverse event occurring outside the DLT window that is determined by the investigator to be possibly related to the investigational product, which is seen more frequently or more severe than expected or is persistent despite appropriate management, can be determined to be a DLT upon unanimous decision by the DLRT after review of the adverse event and all available safety data.

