Subjects who withdraw consent to participate in the study prior to achieving objective response will be censored at their last evaluable radiological assessment date.

End of study:

Primary Completion:

The primary completion of study will occur when the last subject is assessed or receives an intervention for the purposes of final collection of data for the primary analysis. (The primary analysis will occur when target enrollment in Part 1 and Part 2 is complete and each subject either completes 6 months on study or withdraws from the study.)

End of Study:

The time when the last subject is assessed or receives an intervention for evaluation in the study. (The final analysis will occur at this time.)

Enrollment:

A subject is considered enrolled after meeting all eligibility criteria and treatment and cohort have been assigned for the study.

See protocol section 5.0 for further details.

Investigational Product:

The term investigational product is used in reference to AMG 596.

Maximum Tolerated Dose (MTD):

The MTD is defined as the maximum dose with the highest probability of the target toxicity probability interval (TPI), but with a less than 0.25 probability of an excessive or unacceptable TPI.

The target TPI is (0.20, 0.33] and TPIs of (0.33, 0.60] and (0.60, 1.00] are defined as excessive and unacceptable, respectively.

Overall Survival (OS):

The number of days from the date of first administration of AMG 596 to the date of death, regardless of cause.

Subjects who withdraw from treatment without withdrawing consent will be followed for survival status whenever possible. Subjects who are alive (no record of death) and are lost to follow-up will be censored at the date of last contact.

Objective Response (OR):

Tumor response assessment of either complete response or partial response (CR or PR) per modified RANO criteria.

Progression Free Survival (PFS):

The number of days from the date of first administration of AMG 596 to the date of radiological evidence of disease progression (date of MRI scan) or death, regardless of cause.

The following censoring strategies for missing assessment dates will be used for the progression free survival analysis:

If a subject's disease has not progressed and the subject is alive, progression-free survival time will be censored at the last date they are known to be progression-free (ie, the last evaluable radiological assessment date).

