Time to progression is calculated as the number of days from the date of first administration of AMG 596 to the initial date of radiographic progressive disease (PD) per MRI scan (Initial date of first PD – date of first dose of AMG 596+1).

The following censoring strategies for missing assessment dates will be used for the time to progression:

If a subject's disease has not progressed , time to progression will be censored at the last date they are known to be progression-free (ie, the last evaluable radiological assessment date).

If a subject has no tumor evaluation in the study, time to progression will be censored at the date of the first administration of AMG 596.

Subjects who withdraw consent to participate in the study prior to disease progression will be censored at their last evaluable radiological assessment date.

6. Analysis Sets

For all analyses, subjects will be analyzed according to the dose and treatment they received, not the dose and treatment to which they were assigned.

Safety Analysis Set

The analysis of all endpoints, unless noted otherwise, will be conducted on the Safety Analysis Set defined as all subjects that are enrolled and receive at least one administration of AMG 596.

DLT Evaluable Analysis Set

The DLT Evaluable Analysis Set will be used to summarize incidence of dose limiting toxicity (DLT). Subjects are classified as DLT-evaluable if they have had the opportunity to complete the DLT period and:

- Subject in the [REDACTED] cycle receiving a complete first cycle with 100% of the planned doses of investigational product, or
- Subject in the [REDACTED] cycle receiving at least 90% of the planned doses of investigational product or
- Subject that has experienced a DLT

Pharmacokinetic Analysis Set

The pharmacokinetic (PK) analysis set will contain all subjects for whom at least one PK parameter or endpoint can be adequately estimated.

Efficacy Analysis Set

All subjects that are enrolled and receive at least one administration of AMG 596 at the MTD will be included in the analysis of the secondary efficacy endpoints.

RANO Evaluable Analysis Set

All subjects that are enrolled and receive at least one administration of AMG 596 and who have at least one measurable lesion at baseline will be part of this analysis set.

7. Planned Analyses

There are 3 analyses (interim, primary and final) which are planned in the study.

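### SAP v2.0 predates the combination arm: applied to Arm 2, it would drop AMG 404-only events from the DLT and treatment-related AE summaries, and its DLT list differs from the protocol's

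*SAP*

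**What the plan says.** **SAP.** Section 1 ties the plan to the protocol dated 05 July 2017 and covers the interim, primary and final analyses. Section 10 declares nothing changed from the protocol. Section 5 limits a DLT to an event in the first "days in each dose exploration cohort and attributable to AMG 596". The same section states: "The term investigational product is used in reference to AMG 596". Its treatment-related AE is one the investigator judges reasonably possibly caused by the investigational product, so by that definition it means AMG 596. Section 6 says that "subjects will be analyzed according to the dose and treatment they received, not the dose and treatment to which they were assigned". The SAP does not mention AMG 404 or Arm 2.

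**Protocol (Amendment 5, 29 July 2019).** Section 6.2.3 counts a DLT when it is "regarded to be related to AMG 596 and/or AMG 404". Section 6.1 names both agents as investigational products. Section 10.1.1 lists DLTs, treatment-emergent AEs, treatment-related AEs, and changes in vital signs, examinations and laboratory tests as the primary endpoint. Section 10.5.1 says that the analyses "will be reported separately for subjects enrolled to Arm 1 and for subjects enrolled to Arm 2".

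**DLT lists.** Protocol 6.2.3 has three items that SAP section 5 lacks: an exemption for transient, clinically irrelevant laboratory values, an exemption for lymphopenia, and a criterion for grade 3 endocrinopathy that hormone replacement does not control. The amendment log shows all three as Amendment 5 additions.

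**The concern.** AMG 404 is an anti-PD-1 antibody, and the protocol gives a whole appendix (G) to its immune-related reactions. Events that an investigator attributes to AMG 404 and not to AMG 596 are therefore foreseeable in Arm 2. The protocol counts such an event as a DLT if it meets the criteria, and as treatment-related. Read literally, the SAP counts it as neither.

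Two components of the primary endpoint would then carry different definitions in the two governing documents. SAP section 9.6.1 reports DLT incidence and the fitted dose-toxicity curve by dose and group. For Arm 2, that report could rest on fewer events than those used to choose the dose, and would understate the combination's attributed toxicity.

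**Working it through.** **1. One event under both documents.** Take an Arm 2 event that meets a listed criterion within the DLT period and is attributed to AMG 404 only.

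| Component | Protocol | SAP v2.0 |
|---|---|---|
| DLT | counted | not counted |
| Treatment-related AE | counted | not counted |
| Treatment-emergent AE | counted | counted |

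The last row holds because the SAP's treatment-emergent definition has no causality test, and because AMG 404 is first given after the AMG 596 infusion has started (protocol 2.5.3.2).

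**2. The denominator.** Both documents make a subject DLT-evaluable through a required share of planned investigational product (100% or 90%, by cycle type) or through having had a DLT. Under protocol 6.2.4.1 a DLT interrupts AMG 596. A subject who stops for an AMG 404-only DLT is evaluable in the protocol because of that DLT. In the SAP the event is not a DLT, so the subject is evaluable only if enough AMG 596 was given. With x DLTs in n evaluable subjects, one of them AMG 404-only, the protocol gives x/n. The SAP gives (x − 1)/n if the subject remains evaluable and (x − 1)/(n − 1) if not.

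**3. The plan's own figure.** Protocol 10.2 states a 19-56% chance of at least one DLT with 2 subjects and 47-91% with 6, for true rates of 10-33%. The formula is 1 − (1 − p)^n.

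- n = 2: 1 − 0.90² = 19.0%; 1 − 0.67² = 55.1% (55.6% at p = 1/3).
- n = 6: 1 − 0.90⁶ = 46.9%; 1 − 0.67⁶ = 91.0% (91.2% at p = 1/3).

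The stated figures are reproduced.

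**4. The same figure under SAP attribution.** Let f be the share of subjects with a DLT whose only DLT is attributed to AMG 404 alone. The counted rate is p(1 − f). The documents give no value for f, so those below are assumptions. All subjects are kept in the denominator.

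| f | Counted rate at p = 0.10 and 0.33 | n = 2 | n = 6 |
|---|---|---|---|
| 0 | 0.100, 0.330 | 19.0-55.1% | 46.9-91.0% |
| 10% | 0.090, 0.297 | 17.2-50.6% | 43.2-87.9% |
| 25% | 0.075, 0.2475 | 14.4-43.4% | 37.4-81.8% |
| 50% | 0.050, 0.165 | 9.8-30.3% | 26.5-66.1% |

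For example, at f = 50% and n = 6: 1 − 0.95⁶ = 26.5% and 1 − 0.835⁶ = 66.1%.

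**5. The lists.** A grade 3 endocrinopathy that replacement does not control and that lasts 3 days or less is a DLT in the protocol only. Beyond 3 days despite treatment it also meets the SAP's general grade 3 rule, if attributed to AMG 596. The laboratory exemption works the other way: where it applies, it removes a DLT that the SAP list could still count. The net direction of the list differences is therefore not determined.

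**The case against.** The strongest reply is that this is a version gap and not a chosen analysis. The SAP is dated 20 May 2019, about ten weeks before Amendment 5, and plans for 82 subjects on a single agent. Escalation decisions are made by the dose level review team under the protocol, so dose selection need not change. All of that stands. It explains the mismatch but does not remove it, because no other SAP is provided for the interim, primary and final analyses of Arm 2.

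It is also fair that protocol 9.2.2.1 asks one causality question about the investigational product, a term that in the protocol covers both agents. Whether AMG 404-only attribution is recorded separately depends on the eCRF, which is not among the documents. If it is not, the SAP restriction could not be applied as written.

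Several stronger readings are tempting but not supported:

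- **AMG 404-only toxicity leaves the primary endpoint altogether.** It does not. It stays among treatment-emergent AEs and, where relevant, laboratory and vital-sign changes.
- **A transient, clinically irrelevant ALT rise is a DLT in the SAP only.** This is doubtful. A SAP DLT must be an adverse event, and protocol 9.2.2.1 generally does not record laboratory findings without clinical significance as such.
- **The missing lymphopenia exemption matters.** It changes almost nothing, since no hematological criterion in the SAP captures lymphopenia.
- **The treatment-received rule moves Arm 2 subjects who stop before AMG 404 into Arm 1 and inflates the Arm 2 response rate.** The SAP has no arms to move them between, and protocol 10.5.1 already requires reporting by arm enrolled. A clarifying line is enough.
- **The grade 4 enrollment-hold rule is weakened.** That rule stands only in the protocol, where both agents are investigational products.

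**Conclusion.** The point holds for two components of the primary endpoint. If SAP v2.0 is used for Arm 2 as written, events attributed to AMG 404 alone are excluded from DLTs and treatment-related AEs, contrary to protocol 6.2.3 and 6.1. A subject who stops early for such an event may also leave the DLT-evaluable set. Separately, the two DLT lists differ by three items, so a few events could be DLTs in one document only.

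The size cannot be fixed from the documents. It scales with f and is zero if every AMG 404-related DLT is also attributed to AMG 596. Over an assumed 10-50%, the chance of seeing at least one DLT in six subjects falls by about 3 to 25 percentage points, depending on f and the true rate (91.0 − 87.9 = 3.1 at the smallest; 91.0 − 66.1 = 24.9 at the largest). This is the effect on what the SAP would count. It does not show that escalation decisions would be wrong.

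**What to change.** Amend the SAP to Amendment 5 before any Arm 2 analysis:

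1. **Section 5, attribution.** For Arm 2, define investigational product, treatment-related AE and DLT attribution as AMG 596 and/or AMG 404. Carry that meaning into the DLT-evaluable definition in sections 5 and 6.
2. **Section 5, DLT list.** Reconcile it with protocol 6.2.3 so that one list applies, for example by citing that section instead of restating it.
3. **Section 6.** State that reporting is by arm enrolled, as in protocol 10.5.1, with dose level as received.
4. **Sections 1 and 10.** Update the protocol version cited and the statement on departures from the protocol.

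The cost is SAP wording. The definitions themselves need no new data.

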7.2.2 Treatment

All subjects will be hospitalized for the following periods:

Cycle 1:

- For the first [REDACTED] of AMG 596 monotherapy (Arm 1)
- For the first [REDACTED] of AMG 596 in combination with AMG 404 (Arm 2), hence AMG 404 will be administered on [REDACTED]
- For at least 24 hours following completion of AMG 596 cycle 1 for both Arm 1 and Arm 2
- For additional 72 hours after AMG 596 step dose if necessary

Cycle 2 and all subsequent cycles:

- For at least the first 72 hours of AMG 596 infusion in both Arm 1 and Arm 2
- For additional 72 hours after AMG 596 step dose if necessary.

Hospitalization may be shortened to 48 hours from the 6th cycle onwards at the discretion of the investigator.

AMG 404 can be administered in an outpatient setting starting from cycle 1 [REDACTED] onwards. Subjects should be monitored intensely in hospital or outpatient clinic for at least 4 hours after start of each AMG 404 infusion from cycle 1 [REDACTED] onwards.

Restart of the infusion should be performed in the clinic/hospital under the supervision of the investigator or designee and the subject should be hospitalized for a minimum of 24 hours when the infusion interruption meets the following criteria:

- associated to an AE, or
- interruption > 24 hours due to a pump related issue.

[figure not shown]

Dosing with AMG 596 or AMG 596 in combination with AMG 404 can continue unless the subject becomes intolerant to investigational product, the signs and symptoms of clinical progression are evident as determined by the investigator, or the subject withdraws consent. Tumor evaluations by MRI will occur every 10 to 12 weeks from start of treatment. Earlier assessments can be made if clinically indicated at the discretion of the managing physician. Modified RANO criteria ([Appendix D](#)) will be used allowing subjects to stay on study until clinically significant disease progression if no other treatment discontinuation criteria apply. Upon discussion with the Sponsor, subjects may continue to receive treatment after radiographic confirmation of progressive disease as long as they continue to derive clinical benefit in the opinion of the investigator and until further increase in tumor burden. For analysis purposes, date of PD is the date of initial observed PD.

Investigational product is to be administered after all other protocol required pre-dose assessments have been performed on day 1 of each cycle.

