If a subject has no tumor evaluation in the study, progression-free survival time will be censored at the date of the first administration of AMG 596.

Subjects who withdraw consent to participate in the study prior to disease progression will be censored at their last evaluable radiological assessment date.

Response Criteria (per modified RANO):

Complete Response (CR):

- Disappearance of all enhancing disease
- No new lesions
- Stable or improved T2/FLAIR
- No more than physiological steroids
- Clinically stable or improved
- Disappearance confirmed with follow-up scan after ≥ 4 weeks

Partial Response (PR):

- $\geq 50\%$ decrease in the sum of perpendicular diameters of enhancing disease from baseline
- Stable or improved T2/FLAIR
- Stable or decreased steroid dose
- Clinically stable or improved
- Decrease confirmed with follow-up scan after ≥ 4 weeks

Stable Disease (SD):

- Changes do not qualify for CR, PR or PD
- Stable or improved T2/FLAIR
- Stable or decreased steroid dose
- Clinically stable or improved

Progressive Disease (PD):

Any of the below

- $\geq 25\%$ increase in the sum of perpendicular diameters of enhancing disease from the lesser of baseline or nadir
- Or substantially worsened T2/FLAIR
- Or unequivocal progression in new lesions
- Or substantial clinical decline
- Increase confirmed with follow-up scan ≥ 4 weeks after initial observation.

Screening Date:

Screening date is defined as the date the informed consent was signed.

Study Day 1:

Day 1 is defined as the first day that investigational product is administered to the subject. The day before Day 1 is referenced as Day-1.

Study Day:

Post day of dose: study day = (study date - date of Study Day 1) + 1

Pre day of dose: study day = (study date – date of Study Day 1)

Time to Response:

Time to response is calculated as the number of days from the date of first administration of AMG 596 to the date of confirmation of first objective response per MRI scan (date of confirmation of first objective response – date of first dose of AMG 596+1).

If a subject did not respond, time to response will be censored at the date of the last evaluable response assessment.

If a subject has no tumor evaluation related to response assessment as per modified RANO criteria, time to response will be censored at the date of the first administration of AMG 596.

Time to Progression:

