9.5 Efficacy Analyses

Unless otherwise specified, all subjects that are enrolled and receive at least one administration of AMG 596 at the MTD (the efficacy analysis set) will be included in the analysis of the secondary efficacy endpoints.

The following methods will be used with Kaplan-Meier analyses of efficacy endpoints.

- Estimation of the median and CI will use the Brookmeyer and Crowley (1982) method
- Landmark estimates (eg, 6 month PFS) will be estimated using the Kaplan-Meier curve and CI using Greenwood's formula to estimate the standard error (see [Kalbfleisch J.D. and Prentice R.L. \(1980\)](#))

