9.5.1 Analyses of Efficacy Endpoint(s)

Duration of Response:

Descriptive statistics will be provided. As appropriate, duration of response will be analyzed using the Kaplan-Meier method. Kaplan-Meier curves and estimates will be presented. Subjects without an objective response are excluded from the analyses of this endpoint. The median duration of response and other percentiles, as appropriate, and 80% CI will be presented. The percent of subjects with durable response at 6 and 12 months along with 80% CI will be presented.

Time to Response:

Descriptive statistics will be provided. As appropriate, time to response will be analyzed using the Kaplan-Meier method. Kaplan-Meier curves and estimates will be presented. The median time to response and other percentiles, as appropriate, and 80% CI will be presented.

Time to progression:

Time to progression will be analyzed using the Kaplan-Meier method. Kaplan-Meier curves and estimates will be presented. The median time to progression and other percentiles, as appropriate, and 80% CI will be presented. The percent of subjects who are progression-free at 6 and 12 months along with 80% CI will be presented.

Objective Response Rate:

Objective Response Rate will be analyzed using RANO Evaluable Analysis Set.

The number and proportion of patients with an objective response will be tabulated by AMG 596 dose received (MTD or other doses). An exact 80% confidence interval will be calculated using Clopper-Pearson method ([Clopper and Pearson, 1934](#). See [Appendix B](#) for code fragment) for the OR rate for all subjects in part 2 and those in part 1 treated at RP2D/MTD for each group.

Progression Free Survival:

Progression free survival (PFS) will be analyzed using the Kaplan-Meier method. Kaplan-Meier progression free survival curves and estimates will be presented. The median PFS and other percentiles, as appropriate, and 80% CI will be presented. The percentage of subjects alive and progression-free at 6 and 12 months along with 80% CI will be presented.

Response Criteria:

Response criteria will be analyzed using RANO Evaluable Analysis Set.

The number and percentage of subjects in each response category (CR, PR, SD and PD) will be tabulated by AMG 596 dose received (MTD or other doses).

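### The SAP counts death as a PFS event, but its no-evaluation censoring rule omits the alive condition, so applied as written a death before any post-baseline MRI is censored on day 1

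*SAP*

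**What the plan says.** SAP Section 5 (Definitions), under Progression Free Survival, runs the clock from the first dose of AMG 596 "to the date of radiological evidence of disease progression (date of MRI scan) or death, regardless of cause". Death is therefore an event. The censoring rules that follow, introduced as handling missing assessment dates, include:

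- **Not progressed:** "If a subject's disease has not progressed and the subject is alive, progression-free survival time will be censored at the last date" the subject was known to be progression-free. This rule is limited to living subjects.
- **No evaluation:** "If a subject has no tumor evaluation in the study, progression-free survival time will be censored at the date of the first administration". This rule has no condition on vital status.

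No sentence says which text governs when a subject without a tumor evaluation has died.

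The rules feed the reported rates. SAP 9.5 says "Landmark estimates (eg, 6 month PFS) will be estimated using the Kaplan-Meier curve", and SAP 9.5.1 adds "The percentage of subjects alive and progression-free at 6 and 12 months along with 80% CI will be presented". Protocol 10.5.3 instead plans a simple proportion progression-free at 6 and 12 months with an exact 80% CI, while SAP Section 10 reports no changes from the protocol's analyses.

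On timing, Protocol 7.2.2 states "Tumor evaluations by MRI will occur every 10 to 12 weeks from start of treatment". Earlier scans are allowed if clinically indicated. Protocol 7.2.4 adds a scan at safety follow-up if the last one is more than 6 weeks old.

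**The concern.** A subject who dies in the first two to three months with no scan after baseline falls under two contradictory instructions. A programmer who follows the no-evaluation rule literally complies with the SAP, yet takes that subject out of the risk set at time zero and discards the death. These are the earliest failures, so losing them can only flatter the landmark rates.

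The wording suggests that the gap is real. For time to progression, where death is not an event, SAP Section 5 drops the alive condition from the first rule and keeps the no-evaluation rule unchanged. The same no-evaluation rule thus serves one endpoint that counts death and one that does not. PFS is also read without a concurrent control, so an error in one direction is not offset elsewhere.

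**Working it through.** **Plan's own figures.** The documents give no PFS assumption, event count or power, so there is no PFS figure to reproduce. The illustration uses n = 21, the Group 1 number at the RP2D/MTD (6 + 15; SAP 3.2, Protocol 10.2). The figures stated for that n reproduce:
- at least one adverse event at 5% incidence: 1 − 0.95^21 = 65.9% (stated 66%)
- at least 4 responses at ORR 20%: 63.0% (stated 63%)
- exact 80% CI for 4/21: 8.6% to 34.5% (stated 9% to 35%)

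**Effect of the rule.** Let d of n subjects die with no post-baseline scan, and let k be progression-free at the landmark. With no other censoring before it:
- deaths as events: S = k/n
- deaths censored at first dose: S = k/(n − d) = (k/n) × 1/(1 − q), with q = d/n

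| Unscanned deaths | n = 21, k = 5 | n = 31, k = 8 |
|---|---|---|
| 0, or deaths counted as events | 23.8% | 25.8% |
| 1 | 5/20 = 25.0% | 8/30 = 26.7% |
| 2 | 5/19 = 26.3% | 8/29 = 27.6% |
| 3 | 5/18 = 27.8% | 8/28 = 28.6% |
| 4 | 5/17 = 29.4% | 8/27 = 29.6% |

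Here k is illustrative, and n = 31 is the Group 2 maximum per arm in Protocol 10.2. The Greenwood SE for 5/21 is √(0.238 × 0.762/21) = 9.3 points. The largest shift at n = 21 is 29.4 − 23.8 = 5.6 points.

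**Range for q (assumption).** No document gives q. Protocol 2.1 cites a randomized nivolumab trial in first-recurrence glioblastoma with median OS 9.8 months and 12-month OS 42%. Under a constant hazard, and if no early death is scanned:
- median 9.8 months: 1 − 0.5^(2.30/9.8) = 15.0% dead by week 10, and 1 − 0.5^(2.76/9.8) = 17.7% by week 12
- 12-month OS 42%: 15.3% by week 10 and 18.1% by week 12

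That is 3 to 4 of 21 subjects. It is total early mortality in another trial, so it serves only as a ceiling. The factor 1/(1 − q) is 1.05 at q = 5%, 1.11 at 10%, 1.18 at 15% and 1.22 at 18%.

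**Protocol version.** In a simple proportion, an early death stays in the denominator. If it counts as not progression-free, the estimate remains k/n whatever d is.

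**The case against.** The strongest reply is that the definition already settles the matter. Death from any cause is an event, the reported quantity is the share alive and progression-free, and the censoring rules are introduced for missing assessment dates, whereas a recorded death has a date. A sensible programmer would count it. Strict literalism also proves too much: every subject has a screening MRI, so the no-evaluation rule would never apply unless it is read as post-baseline.

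This shows that the SAP can be read the other way, so a reader who infers that early deaths certainly drop out, or that PFS is already known to be overstated, goes further than the text. It does not remove the conflict: no sentence gives death precedence, and the neighbouring rule states the alive condition where this one does not.

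On size, three points stand.
- A reader might infer that the whole curve, or the median, rises by 1/(1 − q). It does not. The factor applies only after all such deaths have occurred and without other earlier censoring. Under the constant-hazard assumption with median 9.8 months, 9.3% have died by week 6, so if those deaths are the only events so far the ratio there is 1/(1 − 0.093) = 1.10. The full factor at q = 16% is 1/(1 − 0.16) = 1.19.
- A reader might take 15% to 18% as the expected q. Several provisions lower it: the 3-month life-expectancy criterion, ECOG 0–1, clinically indicated scans, the safety follow-up scan, MRI on permanent discontinuation for grade 4 neurologic events (Protocol 6.3.2), and the effort to document radiographic progression after neurological decline (Protocol Appendix D). The figure has no stated basis for Group 2.
- PFS is a descriptive secondary endpoint. Futility rests on ORR and enrollment holds rest on adverse events, so no decision rule depends on it.

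**Conclusion.** The conflict between the PFS definition and the no-evaluation rule is real. It should be fixed, but it does not threaten the study's conduct or its primary objective. Applied as written, the rule can move the Kaplan-Meier 6- and 12-month rates in one direction only, upward. The shift is nil if nobody dies unscanned. In the n = 21 illustration it is about 1 to 6 percentage points for one to four such deaths, inside one Greenwood SE.

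These sizes assume no other censoring before the landmark and that all such deaths precede it. The ceiling of 15% to 18% for q applies only to recurrent disease and assumes early mortality no worse than in the cited trial.

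**What to change.** In SAP Section 5, Progression Free Survival, replace the no-evaluation rule with:

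*If a subject has no post-baseline tumor evaluation and has no recorded death, PFS is censored at first dose; if the subject died without a post-baseline tumor evaluation, death is a PFS event on the date of death.*

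Adding post-baseline also removes the difficulty that every subject has a screening MRI. Leave the matching time-to-progression rule unchanged, because death is not an event for that endpoint. In the same edit, reconcile the Kaplan-Meier landmarks in SAP 9.5 with the proportion in Protocol 10.5.3, or list the difference in SAP Section 10.

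The PFS rule costs one SAP sentence, with no new data and no design change. If unscanned deaths occur, the reported PFS will be slightly less favourable than under the literal rule.
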